4.4.1.1. Serious Adverse Event

An AE will be counted as a *serious adverse event* (SAE) if the Clinical Investigator selected “Yes” to the question ‘Is the adverse event serious?’ on the AE eCRF. Any AE is considered a SAE if it fulfills one or more of the following criteria:

- Death (i.e., the AE caused or led to death)
- Life threatening (i.e., immediately life-threatening)
- It required or prolonged inpatient hospitalization.
- It resulted in a persistent or significant disability/incapacity (i.e., the AE resulted in a substantial disruption of the subject’s ability to carry out normal life functions).
- It resulted in a congenital anomaly/birth defect in the offspring of a study subject who was exposed to study therapy prior to conception or during pregnancy.
- It is a medically significant event(s), which may include “sight-threatening events,” that may not meet any of the above serious criteria but may jeopardize the subject or require medical or surgical intervention to prevent one of the outcomes listed above.

4.4.1.2. Ocular Adverse Event

An AE will be counted as an *ocular AE* if the Clinical Investigator selected “OD”, “OS”, or “OU” under ‘Eye(s) affected’ on the AE eCRF.

4.4.1.3. Suspected Adverse Reaction

An AE will be counted as a *suspected adverse reaction* (SAR) if the Clinical Investigator answered ‘Related’ to the AE eCRF question “Relationship to Study Drug”.

4.4.1.4. Events of Special Interest

Events of special interest (ESI) are pregnancy, clinically significant study medication administration error, and macular edema/cystoid macular edema.

4.4.2. Other Safety Measures

[Table 4](#) lists the safety measures to be evaluated for this study.

Table 4: Safety Assessments

Safety Measures	Note
BCVA	Best-corrected visual acuity will be measured for each eye at each visit under normal room illumination using visual acuity chart (e.g., ETDRS chart) and the logMAR scoring will be recorded in the subject’s source document. Increase in logMAR scores means worsening in visual acuity.

Table 4: Safety Assessments (Continued)

Safety Measures	Note
Slit-lamp Biomicroscopy	Slit-lamp biomicroscopy examinations (severity scores for 12 parameters: lid hyperemia, lid edema, conjunctival hyperemia, conjunctival chemosis, corneal staining, corneal edema, keratic precipitate, anterior chamber cells, anterior chamber flare, anterior synechiae of iris, posterior synechiae of iris, and cataract) will be performed and graded right before the 8:00 IOP measurement at all visits except Visit 1/1a (Screening or mid washout visit). Cataract severity will be assessed for subjects with phakic lens.
Ophthalmoscopy	The ophthalmoscopy (fundus) examination will be performed for each eye at Visit 1, Visit 2, and Visit 5 Study Exit/Early Termination. Variables from ophthalmoscopy are cup-to-disc ratio, glaucomatous optic nerve severity, and assessments of vitreous, retina, macula, and choroid.
Eyelid Sulcus, Eyelid, and Iris Color	The investigator (or his/her designee) will take front view and side view photograph of each eye at Visit 2 (Baseline). The photographs must include iris, eye lids and eyelashes of each eye. The photographs taken at Visit 2 (Baseline) will be used to help the Investigator assess any changes (“No changes”, “Increased”, or “Decreased”) from baseline in eyelid, eyelashes, and iris color at each follow-up visit, and assess for DUES (“Yes”, “No”) at Visit 5 Study Exit/Early Termination.
Vital Signs	Resting blood pressure and pulse rate will be collected at Visit 1, Visit 2, and Visit 5.

4.5. Other Definitions

4.5.1. Prior and Concomitant Medications

Non-study medications will be categorized into prior medications and concomitant medications. Specifically, *prior medication* is defined as any non-study medication taken and ended prior to the study medication start date. *Concomitant medication* is defined as any non-study medication taken concurrently while receiving study medication, i.e., the treatment period (period of time from first dose to last dose) of a concomitant medication taken by a subject must overlap with the treatment period (period of time from first dose to last dose) of the study medication.

All prior and concomitant medications will be coded using the World Health Organization (WHO) Drug Global, Version September 2018, format B3. Each prior or concomitant medication will be classified using the Anatomical-Therapeutic-Chemical (ATC) classification system and mapped to a WHO Drug preferred drug name.

4.5.2. Concurrent Medical Conditions

Concurrent medical conditions are those ongoing conditions or diseases that are present at the signing of informed consent.

5. STUDY POPULATION

5.1. Intent-to-Treat Population

The *Intent-to-Treat* (ITT) population will include all randomized subjects.

5.2. Safety Population

The Safety Population will include all randomized subjects who received at least one dose of the study medication. Safety analyses will be performed using the Safety Population and summarizing by actual treatment received.

5.3. Full Analysis Set

The Full Analysis Set (FAS) will include all randomized subjects who received at least one dose of study medication and provided Baseline IOP data (at any timepoint) and at least one post-baseline IOP measurement (at any timepoint). Efficacy analyses will be performed using the FAS and summarized by treatment as randomized.

5.4. Per-Protocol Set

The Per-Protocol Set (PPS) is a subset of the FAS. It will be the analysis population for sensitivity analyses and will be summarized using treatment as randomized. Any subject affected by a significant protocol deviation that might affect the primary efficacy analysis will be excluded from the PPS. The PPS will be identified before the unmasking of treatment assignments.

Before the unmasking of treatment assignment, Santen's study team will review all protocol deviations, identify subjects with any protocol deviation that could impact the efficacy outcome, and determine whether or not to exclude the subject from the PPS.

6. GENERAL CONSIDERATIONS

All measures will be summarized by treatment (planned or actual received) descriptively. Continuous variables will be summarized using descriptive statistics such as number of observations (n), mean, standard deviation, median, minimum, and maximum. Categorical variables will be tabulated using frequency (n) and percent (%).

The statistical testing will be conducted at a significance level of 0.05 (two-sided) and the 95% confidence interval will be shown, unless specified otherwise. No statistical testing will be conducted for safety measures.

All data manipulations, descriptive summaries, and statistical hypothesis testing will be performed using Statistical Analysis System (SAS) Version 9.4 or later.

6.1. Adjustments for Covariates

In general, the inferential analysis of each IOP endpoint will adjust for the baseline IOP. Detailed information on covariate adjustment is provided in [Section 8.1](#).

6.2. Handling of Missing Data

6.2.1. Efficacy Measures

For subjects with the use of any non-study IOP-lowering therapy to lower IOP, unless otherwise specified, the IOP data collected after the non-study IOP-lowering therapy will be censored (treated as missing) in efficacy analyses.

For each IOP endpoint, no imputation is needed for the analysis on observed cases using the mixed-effects model for repeated measures (MMRM). Sensitivity analysis will be performed using a Pattern-Mixture Model (PMM) approach.

In the PMM approach, Multiple Imputation (MI) with mixed missing data mechanisms will be used to investigate the appropriateness of the missing at random (MAR) assumption for missing values resulting from censoring due to the use of IOP-lowering rescue therapy, or resulting from study discontinuation due to lack of efficacy or AE.

6.2.2. Safety Measures

Descriptive summaries of safety measures will be based on observed data only. No imputation of missing scores will be implemented.

6.2.3. Dates for Medical Events and Medications

Completely or partially missing onset and resolution dates of medical history (MH), AE, and concomitant medications (CM) will be imputed as follows ([Table 5](#)):

Table 5: Handling of Missing Date for Medical Events and Medications

Date	Type of Missing Date	Handling of Missing Date
Event onset date (e.g., YYYY-MM-DD)	Completely missing	No imputation will be applied: For AE, the event will be considered treatment emergent. For CM, the event will be considered concomitant. For MH, the event will be considered to occur prior to Inform Consent date.
	Only YYYY is available	Use the first date of YYYY to impute the missing month and day of the onset date.
	YYYY and MM are available, but DD is missing	Use the first date of MM to impute the missing day of the onset date.
Event resolution date (e.g., YYYY-MM-DD)	Completely missing	No imputation will be applied. The event will be considered ongoing (i.e., not resolved) at the last visit date.
	Only YYYY is available	Use the last date of YYYY to impute the missing month and day of the resolution date.
	YYYY and MM are available, but DD is missing	Use the last date of MM to impute the missing day of the resolution date.

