### 21.3.1. Demographics, Medication/Therapy and Medical History

Demographics including age, sex, race, prostaglandin analogs naïve status, and ethnicity will be obtained through subject interviews at Visit 1 (Screening).

Medications and procedures/therapies will be confirmed through subject interviews during the study.

Following details of prior medication that has been used for glaucoma or OHT within 28 days before the date of Visit 1, or any concomitant medication, must be recorded in the subject's source documents.

- Name of medication, route of administration, treated eye(s) (if applicable), dose, frequency, indication, start date and stop date

Following details of prior procedure/therapy that has been received for glaucoma or OHT within 28 days before the date of Visit 1, or any concomitant procedure/therapy, must be recorded in the subject's source documents.

- Name of procedure/therapy, treated eye(s) (if applicable), indication, start date and stop date

Medical history including all lifetime ocular medical history to the extent possible, non-ocular medical history within 5 years, diagnosis, ocular surgical history, current ocular and systemic conditions will be confirmed through subject interviews at Visit 1 (Screening) to determine if the subject meets eligibility criteria. Primary diagnosis and the affected eye must be recorded in the subject's source documents.

- Name of concurrent disease and affected eye(s) (if applicable) will be confirmed at Visit 1 (Screening) and Visit 2 (Baseline), and recorded in the subject's source documents.

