4.4. Safety-Related Definitions

4.4.1. Adverse Event

Under Protocol 011710IN, an AE is defined as any untoward medical occurrence that occurs in a study subject, regardless of the causal relationship with the study treatment. An *on-study* AE can occur any time after the date of informed consent through the last study visit. An AE will be considered as *treatment-emergent* if the onset date of the AE occurred on or after the treatment start date till up to 2 days (twice the scheduled dosing interval) after treatment end date.

Treatment-emergent AEs (TEAEs) are a subset of on-study AEs. Both on-study and TEAEs will be collected, but only TEAEs will be tabulated.

The severity of each AE will be graded by the Clinical Investigator as Mild, Moderate, or Severe. AEs will also be rated by the Investigator as to their causality/relationship to the study drug.

Each AE will be classified into a system organ class (SOC) and coded to a preferred term (PT) using Medical Dictionary for Regulatory Activities (MedDRA), version 21.1 published in 2018.

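### SAP Table 5 classes a medication or adverse event with no start date as concomitant or treatment-emergent even when it is known to have ended before first dose (minor)

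*SAP*

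**What the plan says.** SAP 6.2.3, Table 5, has one row for an onset date of which no part is known. It imputes no date and sets a default: "For AE, the event will be considered treatment emergent. For CM, the event will be considered concomitant". Separate rows cover dates with only a year, or only a year and month. The row for a wholly unknown onset carries no condition on the end date.

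The definitions elsewhere in the SAP do depend on when the record ended or began:

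- SAP 4.5.1: a prior medication is "any non-study medication taken and ended prior to the study medication start date". For a concomitant medication, its own period of use "must overlap with the treatment period (period of time from first dose to last dose) of the study medication".
- SAP 4.4.1: an AE is treatment-emergent "if the onset date of the AE occurred on or after the treatment start date till up to 2 days" past the treatment end date. Collection is wider than that, because an on-study "AE can occur any time after the date of informed consent through the last study visit". Only treatment-emergent AEs are tabulated; SAP 9.1 lists the others.

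Protocol 21.3.1 introduces what must be recorded with "Following details of prior medication that has been used for glaucoma or OHT within 28 days before the date of Visit 1". Start and stop dates are both among the required items.

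**The concern.** Table 5 and the definitions disagree on any record with an unknown start and a known end before first dose. The SAP states no order of precedence, so two programmers could each follow the text and produce different tables.

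The design makes the medication case plausible. Subjects on IOP-lowering drugs stop them 7 to 28 days before baseline, depending on class, and the first study dose is at 20:00 on Day 1. The stop date is thus fixed by the washout, while the start may lie years back and rest on a subject interview.

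What is at stake is descriptive:

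- SAP 7.5 tabulates and lists prior and concomitant medications separately, so a misclassified drug makes both outputs wrong.
- Protocol 9.2.1 prohibits other ocular hypotensives during the study. A washed-out drug shown as concomitant would look like prohibited use.
- An AE that was over before treatment began would move from the listing of non-treatment-emergent events into the AE tables.

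**Working it through.** The plan has no figure to reproduce here. The check applies the Table 5 row and the definitions to the same records and compares the answers.

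**Inputs.** Table 5 (SAP 6.2.3); prior and concomitant definitions (SAP 4.5.1); treatment-emergent definition (SAP 4.4.1); study-day convention (SAP 4.1.4), in which the treatment start date is Day 1 and the day before is Day -1.

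**Logic of the definitions.**

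- Medication: if stop < treatment start, it ended before first dose and is prior. Its period of use cannot overlap the treatment period, so it is not concomitant. The start date is not needed.
- AE: onset ≤ resolution. If resolution < treatment start, then onset < treatment start, and the event is not treatment-emergent. The onset date is not needed.

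**Case by case.**

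| Start / onset | Stop / resolution | Table 5 row | Definitions | Conflict |
|---|---|---|---|---|
| Unknown | Day -28 | Concomitant / treatment-emergent | Prior / not treatment-emergent | Yes |
| Unknown | Day -1 | Concomitant / treatment-emergent | Prior / not treatment-emergent | Yes |
| Unknown | Day 1 | Concomitant / treatment-emergent | Cannot be ruled out | No |
| Unknown | Day 40 | Concomitant / treatment-emergent | Cannot be ruled out | No |
| Unknown | Unknown | Concomitant / treatment-emergent | Cannot be ruled out | No |
| Day -400 | Day -28 | Row does not apply | Prior / not treatment-emergent | No |

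The conflict is confined to a wholly unknown start combined with an end before first dose. In the other unknown-start cases the default is sensible, since nothing places the record before treatment.

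**Partly known end dates.** Table 5 imputes a partial resolution date to the last day of the known month or year, the latest day it could be. If that imputed date is still before treatment start, so is the true date. An end-date check can therefore use imputed dates without wrongly removing a record.

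**Size per record.** Medication and AE tables count a subject once per row. At the planned 200 per arm, one affected subject changes a row by at most 1/200 = 0.5 percentage points. The number of affected records is not in the documents and cannot be derived from them.

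**The case against.** Several points on the other side have weight.

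- *The definition already settles the medication case.* SAP 4.5.1 makes a drug prior from its stop date alone, so Table 5 can be read as a default only for records whose status is otherwise undetermined. That is a sensible reading, and a careful programmer might adopt it. But the row is unconditional and nothing says that 4.5.1 overrides it.
- *Few records can be affected.* The protocol asks for both dates, and a start known only to the year falls under another Table 5 row. An AE that resolved before first dose must have begun after consent, within a screening period of up to 35 days, so a wholly unknown onset would be unusual. This stands, and it limits the size of the problem.
- *The default is conservative.* Protocol 14.5 calls for conservative handling of missing dates. That justifies over-calling when timing is uncertain. It does not cover an event known to have ended before treatment, and for medications there is no evident conservative direction.
- *Deviations are reviewed by people.* Under SAP 5.4 and 7.4, exclusion from the per-protocol set rests on the study team's review before unmasking, not on an automatic concomitant flag. This stands.

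A reader might also infer that a washed-out glaucoma drug relabelled as concomitant would cause the subject's IOP values to be censored. SAP 6.2.1 says that, after use of such therapy, "the IOP data collected after the non-study IOP-lowering therapy will be censored (treated as missing) in efficacy analyses", and it does not state that the therapy must follow first dose. The documents do not support the inference. No censoring statement (SAP 6.2.1, 8, 8.1.2 and 8.2; Protocol 14.7) refers to the concomitant class or to Table 5. SAP 6.2.1 itself goes on to describe the trigger as rescue therapy. Table 5 imputes no start date for these records, so it supplies no date from which to censor. The missing time limit in 6.2.1 would apply equally to washed-out drugs with complete dates, so Table 5 does not cause it.

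**Conclusion.** The inconsistency is real and can be read directly from the text. For a record with a wholly unknown start and an end before first dose, Table 5 gives a class that SAP 4.5.1 and 4.4.1 rule out. The conclusion assumes only that Table 5 is applied as written.

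The effect is limited to the prior and concomitant medication outputs and the treatment-emergent AE tables. These are descriptive, and SAP section 6 plans no testing of safety measures. The number of records may be small or zero. No effect on IOP censoring, the nine-timepoint comparison or any key secondary test is shown. Severity: minor.

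**What to change.** In the Table 5 row for a wholly unknown onset date, replace the AE and medication defaults with: *If the end date, known or imputed under this table, is before the treatment start date, the medication is prior and the AE is not treatment-emergent; otherwise the medication is concomitant and the AE is treatment-emergent.* The medical-history default in that row can stay as it is.

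The cost is one SAP sentence and one programming condition, applied to the medication and AE derivations. No protocol text, data collection or efficacy analysis changes. Records that are truly ambiguous keep their present class.

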#### **12.1.1.2. Reporting Adverse Events**

AEs, whether spontaneously reported by the subject or noted by authorized study personnel, will be recorded in the subject's medical record and on the appropriate AE electronic case report form (eCRF). Each recorded AE will be described by its duration (represented in dates), affected eye(s) (if applicable), maximum severity of the AE, seriousness criteria, suspected relationship to the study medication, actions taken with the study medication and the study participation, outcome of the AE, and any other attributable causes of the AE.

Regardless of relationship to the clinical study, AEs that occur at any time after the subject has provided written informed consent until subject withdrawal or the scheduled exit visit, must be recorded. To improve the quality and precision of acquired AE data, Investigators should observe the following guidelines:

- Whenever possible, use recognized medical terms when recording. Do not use colloquialisms and/or abbreviations.
- If known, record the diagnosis (i.e., disease or syndrome) rather than component signs and symptoms and /or laboratory or test findings (e.g., record congestive heart failure rather than dyspnea, rales, and cyanosis, and enlarged heart on chest x-ray). However, other events that are considered unrelated to an encountered syndrome or disease should be recorded as individual AEs (e.g., if congestive heart failure and severe headache are observed at the same time and are clinically unrelated, each event should be recorded as an individual AE).

- If the diagnosis is not known, then record the leading component sign, symptom or test finding and describe the other clinically related findings in the narrative description of the case. A suspected diagnosis can be used and described as such (e.g., record suspected or probable myocardial infarction); this has to be updated in the clinical database once the diagnosis is confirmed.

AEs occurring secondary to other events (e.g., sequelae) should be identified by the primary cause. A primary AE, if clearly identifiable, generally represents the most accurate clinical term. If a primary AE is recorded, events occurring secondary to the primary event should be described in the narrative description of the case. For example:

The subject developed orthostatic hypotension and subsequently fainted and fell to the floor wherein she experienced a head trauma and neck pain.

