### **14.5. Handling of Missing Values**

The primary analysis of continuous IOP endpoints will be performed using the MMRM analysis on observed cases. As sensitivity analyses, a last-observation-carried-forward (LOCF) approach and a Pattern Mixture Models (PMM) approach may be applied to evaluate the impact of missing data on the primary analysis results. For the binary IOP endpoints, the missing data at Month 3 will be imputed using an LOCF approach.

For medical events including AEs and medical history, completely or partially missing onset and resolution dates will be imputed in a conservative fashion. Same rules will be followed to impute the completely or partially missing start and end dates of non-study medications.

Unless specified otherwise, descriptive summaries will be based on observed cases.

More details on handling of missing data will be provided in the SAP.

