9.1. Adverse Events

AEs, SAEs, SARs, serious SARs, and significant AEs (AEs leading to study drug discontinuation and AEs leading to death) will be tabulated by type of AEs by treatment arm using actual treatment received for all AEs, ocular AEs, and non-ocular AEs separately.

Besides the overall AE summary, AEs, SAEs, SARs, serious SARs will be tabulated by SOC and preferred term for all AEs, ocular AEs, and non-ocular AEs separately. A subject who experienced multiple AEs within a SOC or preferred term will be counted only once for that SOC or preferred term. Non-serious AEs (including number of events) and ESIs will also be summarized by SOC and preferred term.

AEs, SAEs, SARs, serious SARs, ocular AEs, AEs leading to death, AEs leading to study drug discontinuation, non-TEAEs, and ESIs, if any, will be listed separately.

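### SAP Table 5 can date an on-treatment adverse event before first dose when its onset date is partial, which removes it from the TEAE tables

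*SAP*

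**What the plan says.** SAP section 6.2.3, Table 5, gives three rules for an event onset date.

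- Day missing: "Use the first date of MM to impute the missing day of the onset date".
- Month and day missing: "Use the first date of YYYY to impute the missing month and day of the onset date".
- Completely missing: nothing is imputed, and "For AE, the event will be considered treatment emergent".

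Section 4.4.1 makes an adverse event treatment-emergent when its onset lies between the treatment start date and 2 days after the treatment end date. It adds: "Both on-study and TEAEs will be collected, but only TEAEs will be tabulated". Under section 9.1, events that are not treatment-emergent still appear in a listing: "AEs leading to death, AEs leading to study drug discontinuation, non-TEAEs, and ESIs, if any, will be listed separately".

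Protocol section 14.5 sets the principle that "completely or partially missing onset and resolution dates will be imputed in a conservative fashion". It does not define the term and leaves the details to the SAP. Protocol section 12.1.1.2 requires recording of "AEs that occur at any time after the subject has provided written informed consent until subject withdrawal or the scheduled exit visit", so collection begins before first dose.

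**The concern.** The two partial-date rules never compare the imputed date with the treatment start date. Take an event that truly began on treatment but whose record gives only the month of first dose. Table 5 moves it to the 1st of that month, which precedes first dose unless dosing began that day. Section 4.4.1 then denies it treatment-emergent status and the tables omit it. A year-only date in the year of first dose fares the same way unless dosing began on 1 January; a start on the 1st of any other month does not rescue it. No other section restores the status.

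Table 5 also disagrees with itself in direction. An onset about which nothing is known is treated as treatment-emergent, while an onset known to fall in the month of first dose is not. Less information gives the more cautious answer.

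At stake is the completeness of the TEAE tables for events soon after first dose. There is a side effect in sections 9.1.1 to 9.1.3, where start times of ocular inflammation, macular edema and cosmetic changes are summarised in study days: an affected event is either left out or enters with a negative study day.

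**Working it through.** The plan gives no figure to reproduce, so the check applies its rules to dates.

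**Example.** First dose 20 November; onset recorded as November of that year. Imputed onset: 1 November. By SAP section 4.1.4, study day = 1 November − 20 November = −19. The event is not treatment-emergent, even if it began on, say, 25 November.

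**Inputs.** Table 5 and the section 4.4.1 definition (SAP); Day 91 as the Month 3 target (protocol section 7.4). Assumptions: first-dose dates uniform over a 365-day year, true onsets uniform over Days 1 to 91, and dates equally likely to be partial throughout. The total is 365 × 91 = 33,215 combinations of start date and onset day.

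**Day missing.** For a start on day d of an n-day month (d ≥ 2), the n − d + 1 on-treatment days left in that month are lost. Summed over d, this is n(n − 1)/2 per month.

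- All months: 7 × 465 + 4 × 435 + 378 = 5,373 lost combinations; 5,373 / 33,215 = 16.2%.
- Range by start date: 0 (start on the 1st) to 30/91 = 33.0% (start on the 2nd of a 31-day month). Day 30 is the latest day affected.
- Days 1–7: 7n − 28 lost per month, so 7 × 365 − 28 × 12 = 2,219 of 2,555 = 86.8%.
- Days 8–30: 5,373 − 2,219 = 3,154 of 365 × 23 = 8,395, or 37.6%.
- Days 31–91: none.

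**Year only.** A start with r days left in the year (r = 1 to 364, so 1 January is excluded) loses min(91, r) days.

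- Sum: 4,186 + 91 × 273 = 29,029; 29,029 / 33,215 = 87.4%.
- By period: 98.9% in Days 1–7, 94.8% in Days 8–30, 83.3% in Days 31–91.

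Adding the 2-day tail after treatment end changes the overall figures only to 15.8% and 87.1%.

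**What the alternative would get wrong.** If a matching partial date were set to the treatment start date, events that began between consent and first dose would be counted as TEAEs. Suppose consent falls L days before first dose and onsets are uniform over collection days. A start on day d has min(L, d − 1) pre-dose days in the first-dose month. On-treatment days in that month total 5,373 + 365 = 5,738 over all starts.

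| L (days) | Pre-dose days | Pre-dose share, all starts | Alternative wrong (at most), starts on the 1st left out | Current rule wrong, starts on the 1st left out |
|---|---|---|---|---|
| 1 | 353 | 353/6,091 = 5.8% | 353/5,726 = 6% | 94% |
| 7 | 2,219 | 2,219/7,957 = 27.9% | 2,219/7,592 = 29% | 71% |
| 28 | 5,348 | 5,348/11,086 = 48.2% | 5,348/10,721 = 50% | 50% |
| 35 | 5,373 | 5,373/11,111 = 48.4% | 5,373/10,746 = 50% | 50% |

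In the first-dose year the pre-dose shares are 1%, 8%, 25% and 29%. The values of L follow protocol section 7.1: a minimum wait of 1 day, washouts of 7 or 28 days, and a screening period of up to 35 days.

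**The case against.** The strongest reply has four parts.

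1. *No breach of the protocol.* Earliest possible onset with latest possible resolution gives the longest duration, which is one fair meaning of conservative. That stands: the protocol does not settle the matter. It does not explain why completely missing onsets go the other way.

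2. *The alternative is no more accurate after a long washout.* This also stands for day-missing dates: with 28 to 35 days of screening, both rules are wrong about half the time. For late-month starts the alternative can be worse. In a 31-day month with 28 days of screening, a first dose on the 25th leaves 24 pre-dose days of 31 (77%), against 14 of 31 (45%) for a first dose on the 15th. Checking the resolution date helps only partly, because a resolution with its day missing is itself moved to month-end. After long washouts, then, the change is a choice to err toward counting events, the choice the SAP already makes for unknown onsets. The gain in accuracy lies in short screening and year-only dates, and the documents do not give the share of short-screening subjects.

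3. *The percentages may overstate the loss.* Subjects are asked about events at about Day 8, so recall is shortest in the very days most affected. If partial dates become commoner as recall lengthens, 16% is too high. Prompt eCRF entry, source verification and system edits should make partial dates few, and year-only dates rare.

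4. *Little follows from it.* The events remain in the non-TEAE listing; serious events, events leading to death or discontinuation, and events of special interest have listings of their own. Safety is not tested, and both arms are handled alike. All true, and the reason the point is minor. A non-TEAE listing still labels an on-treatment event as something it is not, and the incidence tables still omit it.

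**Conclusion.** The concern holds, as a minor point. The mechanism is certain: it follows from Table 5 and section 4.4.1 read together, and nothing else in the plan offsets it. A stated rule gives a wrong classification for on-treatment events whose partial onset date matches the month or year of first dose.

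The size is not known. The shares of 16% (day missing) and 87% (year only) apply to on-treatment events with partial dates, whose number the documents do not give and which may be close to zero. They rest on uniform start dates and uniform onsets. The effect is confined to descriptive safety tables and leaves every efficacy conclusion unchanged.

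**What to change.** Add one rule to SAP Table 5, for adverse event onset only:

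- If the known month and year (or the year alone) match those of the treatment start date, and the resolution date (after Table 5 imputation, or ongoing) is not before treatment start, impute the treatment start date.
- Otherwise keep the first of the month or year.
- For a completely missing onset, keep treatment-emergent status unless the resolution date is before treatment start.

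The rules for medical history and medications need no change. The cost is a sentence or two in the SAP and a short derivation step. The price is that some events beginning between consent and first dose will be counted as treatment-emergent. The pre-dose shares above are upper limits on that, since events known to have resolved before first dose stay out.
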